### Efficacy data

The objective of this pilot study is to estimate the therapeutic response rate in the patients who receive YF476. The primary endpoint of the clinical response is defined as a 25% reduction in the size or number of endoscopically evident type I gastric carcinoids or a reduction of 25% in the gastric ECL cell density. Secondary endpoints include safety and changes in levels of biochemical markers (eg gastrin, CgA), histologic grade and quantitative PCR for ECL cell-specific products.

All variables will be summarised by descriptive statistics as appropriate. The mean or median of the following variables will be expressed as a percentage change of the mean or median response (as appropriate) compared to the baseline period: number of CgA ir-cells per unit area of mucosa CgAmuc and volume density of CgA ir-cells  $\rho_{CgA}$ ,

The data during the treatment period will be compared with baseline using ANOVA, with visit as fixed effect and subject as random effect. If insufficient data are available, the treatment comparison using ANOVA will not be done. Variables and parameters will be transformed before analysis, as appropriate.

Data from all subjects who complete the study without major protocol deviations will be included in the analysis of efficacy. The primary aim of the trial is to find out if YF476 can cause regression of gastric carcinoid tumours.

Interobserver variability will be reported to both endoscopic and histologic interpretations. A blinded endoscopist, who is unaware of the patient history, dose of YF476, or timing of the endoscopic examination, will review a random sample of endoscopic images to report the size of endoscopic lesions. In addition, a blinded pathologist, who is unaware of the patient history, dose of YF476, or timing of biopsy specimen, will review a random sample of histologic images to report the histologic grade and ECL cell density of the biopsy sample. Kappa statistics will be calculated to report the degree of agreement between the study and blinded endoscopists and between the study and blinded pathologists.

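### Kappa is the only agreement statistic named for lesion size and ECL-cell density, and it gives no reader error in mm or % to set against the 25% response threshold

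*Protocol*

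**What the plan says.** Protocol section 18.1 (Efficacy data) lets a patient respond by either of two criteria. The endoscopic criterion is "a 25% reduction in the size or number of endoscopically evident type I gastric carcinoids". The histological alternative is "a reduction of 25% in the gastric ECL cell density". The section then plans a blinded second reading of part of the material:

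- The blinded endoscopist "will review a random sample of endoscopic images to report the size of endoscopic lesions". Size is the only quantity listed for this reader.
- The blinded pathologist "will review a random sample of histologic images to report the histologic grade and ECL cell density of the biopsy sample".

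The agreement statistic follows: "Kappa statistics will be calculated to report the degree of agreement between the study and blinded endoscopists". The same sentence applies it to the pathologists. No other agreement measure is named, and no categories, cut-points or weights are given for size or density.

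Elsewhere the protocol treats both quantities as numbers. Section 18.1 expresses the "number of CgA ir-cells per unit area of mucosa" and the volume density of these cells as percentage change from baseline. Section 14.14 (Methods) uses biopsy forceps in the images to correct lesion size.

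**The concern.** Of the three re-read quantities, only histologic grade is categorical. For the endoscopists, kappa has no categorical variable to work on unless lesion size is first cut into bands.

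An agreement analysis of size and density should show whether reader error is small compared with a 25% change, because that change makes a patient a responder. It should also show whether one reader is systematically lower, and by how much. Kappa is a unit-free index and does neither. A reader of the trial report could see an acceptable kappa and still not know whether a 25% reduction in a lesion lies within reading error.

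This matters somewhat more here because section 7.9 defends an open trial without a comparator on the ground that the outcome measures are robust, and section 18.2 makes a larger trial follow from favourable results.

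**Working it through.** **Inputs from the protocol.** The 25% threshold, the quantities re-read and the choice of kappa come from section 18.1. The protocol gives no reader error, lesion spread or target kappa, so there is no figure to reproduce.

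**Assumptions.** Lesion size is log-normal with median 5 mm. The between-lesion SD of log size, *b*, is 0.3, 0.5 or 0.8. Each reading carries independent multiplicative error with CV from 5% to 25%. There is no bias between readers, and repeat readings have the same error.

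**Step 1: reader error on the log scale.** s = √ln(1 + CV²).
- CV 10%: s = √ln 1.01 = 0.0998, so √2·s = 0.1411.
- CV 25%: s = √ln 1.0625 = 0.2462, so √2·s = 0.3482.

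**Step 2: what the 25% rule needs to know.** For one lesion with no true change, the chance of a read reduction of at least 25% is Φ(ln 0.75 / (√2·s)).
- CV 10%: Φ(−0.2877 / 0.1411) = Φ(−2.04) = 2.1%.
- CV 25%: Φ(−0.2877 / 0.3482) = Φ(−0.83) = 20.4%.

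The 95% limits of agreement between two readers, as a ratio, are exp(±1.96·√2·s).

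| Reader CV | Limits of agreement | Chance of a false 25% reduction, one lesion |
|---|---|---|
| 5% | ×/÷ 1.15 | below 0.1% |
| 10% | ×/÷ 1.32 | 2.1% |
| 15% | ×/÷ 1.51 | 8.6% |
| 25% | ×/÷ 1.98 | 20.4% |

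The limits track the risk directly and do not depend on lesion spread.

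**Step 3: what kappa reports.** Cut size at 5 mm, the assumed median. The readers agree with probability 1/2 + arcsin(ρ)/π, where ρ = b²/(b² + s²), and chance agreement is 1/2. So kappa = (2/π)·arcsin(ρ).
- b = 0.3, CV 10%: ρ = 0.09 / (0.09 + 0.00995) = 0.900, kappa = 0.71.
- b = 0.8, CV 25%: ρ = 0.64 / (0.64 + 0.0606) = 0.913, kappa = 0.73.

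Simulation with 400,000 lesions per setting gives the same two values. Kappa depends only on reader error relative to lesion spread. Nearly equal kappas therefore go with false-reduction risks of 2.1% and 20.4%, about a tenfold difference.

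**Step 4: does weighting help?** Quadratic-weighted kappa on whole millimetres, simulated for the same two settings, is 0.87 and 0.88. Weighting does not separate them.

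**Step 5: dependence on the categories.** Reader error is held at CV 10% with b = 0.5, and only the categories change (unweighted kappa):

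| Categories | Kappa |
|---|---|
| one cut at 5 mm | 0.82 |
| one cut at 10 mm | 0.78 |
| cuts at 3, 5 and 10 mm | 0.74 |
| whole millimetres | 0.42 |
| effectively unrounded values | about 0 |

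**The case against.** The strongest reply is that the protocol says kappa without saying unweighted, and that weights and bands belong in a statistical analysis plan that is not shown. Much of this stands, and it rules out several stronger readings.

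- **A reader might infer that kappa counts exact matches only, so that a larger error can score better.** That holds for unweighted kappa alone. Take sizes uniform on 2–9 mm read to the whole millimetre. A constant offset of 1 mm gives unweighted kappa −0.14 and an offset of 5 mm gives −0.04, but quadratic weighting gives 0.89 and 0.25, in the right order.
- **A reader might infer that kappa would call good measurements poor.** In the same setting, unweighted kappa is 0.41 at reader SD 0.5 mm and 0.17 at 1 mm. Quadratic-weighted kappa is 0.92 and 0.79, equal to the intraclass correlations (ICCs). Nor is SD 1 mm good against a 25% cut: about 15% of unchanged lesions would be read as at least 25% smaller.
- **A reader might infer that kappa hides a systematic reader difference.** The low or negative values above do signal disagreement. What kappa lacks is the direction and the amount in mm or %.
- **A reader might infer that this is the protocol's only safeguard on measurement.** It is not. Section 14.14 has one blinded pathologist read all samples at the end of the study, and it scales lesion size against forceps. Neither yields an agreement figure, but both address measurement error.
- **A reader might look to agreement on responder status.** That would bear on the threshold, but it needs paired baseline and on-treatment reads, which a random sample of images does not guarantee.

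An ICC also depends on lesion spread, so it cannot replace limits of agreement. Section 18.1 promises interobserver variability in general terms and does not say that kappa is exclusive. Even so, kappa is the only statistic it names. Weights or bands added later would make kappa computable for size and density but would not put reader error on the 25% scale.

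**Conclusion.** The point holds in this limited form: for lesion size and ECL-cell density, the named statistic does not give reader error or bias in units comparable with the 25% response threshold. Weighting or banding does not cure that. For histologic grade, kappa is suitable.

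The size is minor to moderate. This is a reliability report on a subsample in a pilot of up to 10 patients. No decision rule uses kappa, and the estimated response rate does not change.

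The numerical contrast (kappa 0.71 versus 0.73, false-reduction risk 2.1% versus 20.4%) rests on assumed reader CVs, lesion spreads and a 5 mm cut. The risk is for a single lesion read twice with independent error, not for a patient's overall response. It shows that kappa cannot distinguish these cases, and it does not predict this trial's reader error.

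**What to change.** Replace the kappa sentence in section 18.1 with wording to this effect, and carry it into the statistical analysis plan:

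- **Lesion size and ECL-cell density:** report the mean between-reader difference with 95% limits of agreement on the log scale, back-transformed to percentages and shown beside the 25% threshold. An ICC may be added as an optional supplement. Readings where one reader sees no lesion cannot be logged and should be counted separately.
- **Histologic grade:** keep kappa, preferably weighted, with the weights stated.

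The cost is one protocol sentence and a little more analysis. The same second reads are used, with no new data and no change to the response analysis.

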# Safety data

Data from all subjects who received any trial treatment will be included in the analysis of safety.

Numerical data will be summarised using means or medians, and other descriptive statistics, according to the type and distribution of the data. Adverse events (see Section 16) will be listed and relationship to treatment assessed.

## Pharmacokinetic data

Plasma YF476 concentrations will be used to determine if there is a relationship between YF476 dose and plasma CgA concentration or serum gastrin concentration.

# 18.2 Determination of sample size

The trial is an exploratory, open, pilot trial, so a power calculation is inappropriate. Gastric carcinoids are a rare condition, so the protocol sets a limit of up to 10 patients.

The results will be reviewed regularly, and if the results are unfavourable, the study will be stopped. If the results are favourable, the sponsor will set up a larger trial, probably double-blind, randomised, and placebo-controlled in design, and with a fixed dose of YF476.

# 19 Ethical and regulatory requirements

The trial proposal will be reviewed by a recognised REC, and by the MHRA. The trial will not proceed unless the sponsor obtains from the MHRA a clinical trial authorisation (CTA), and the main REC approves the trial. The trial will not proceed until a site-specific assessment has been done by a REC and approval for the site has been given.

The trial will be done in compliance with EU Directives 2001/20/EC and 2005/28/EC, The Medicines for Human Use (Clinical Trials) Regulations 2004 and current amendments, the Declaration of Helsinki (South Africa Revision, 1996), GMP, the standard operating procedures issued by NRES for RECs in the UK, and Good Clinical Practice.

All patients must give written consent to participate in this trial. The trial-specific Information and Consent Form will be signed by the patient before any screening evaluation. Before giving consent, subjects must read the information sheet about the trial. They must also read the consent form. They will then discuss the trial with the investigator or his deputy and be given the opportunity to ask questions. The trial-specific Information and the Consent Form must have been approved by the main REC.

Each patient is free to withdraw from the trial at any time, without giving a reason. If a patient withdraws, the investigator will ask the patient to consent to a follow-up

examination. For withdrawn patients, the investigator will use a special Information and Consent Form. If the patient consents to the follow-up examination but asks the investigator to destroy all identifiable samples taken from the subject and/or not enter into the CRF results of the follow-up examination, the investigator will comply with the patient's requests.

The sponsor will ensure that the MHRA and the main REC are informed promptly of SUSARs (see Section 16.3), and that any new reports of SUSARs from other ongoing trials of the IMPs under investigation in this trial are notified to the MHRA, and to the main REC, if applicable. The sponsor will provide the investigator, the main REC and the MHRA with annual safety reports of each IMP under investigation, and listings of all suspected serious adverse reaction (SSAR) reports. If applicable, the sponsor will also provide the investigator, the main REC and the MHRA with 6-monthly safety reports, including listings of all SUSARs.

The investigator will promptly inform the sponsor and chief investigator of any SAE that occurs during this trial (see Section 16.3). The chief investigator will in turn inform the main REC, if applicable (see Section 16.3). The chief investigator will provide the main REC with annual progress reports of the trial, if it lasts longer than a year.

The investigator will report to the sponsor and chief investigator any protocol deviation that is, in his opinion, of clinical significance. The investigator will also inform the sponsor and chief investigator in the event of several deviations which, although of no clinical significance, cause inconvenience and/or discomfort to the volunteers. The chief investigator will in turn promptly inform the main REC.

The sponsor will notify the MHRA and main REC of any serious breach of Good Clinical Practice (for example, the investigator puts subjects' safety at risk, falsifies data, or persistently fails to comply with this protocol or Good Clinical Practice).

Within 90 days after the end of the trial, the sponsor will ensure that the main REC and the MHRA are notified that the trial has finished. If the trial is terminated prematurely, those reports will be made within 15 days after the end of the trial.

The sponsor will supply a summary report of the clinical trial to the MHRA and main REC within 1 year after the end of the trial.

Trial procedures will be subject to audits by the sponsor to ensure compliance with the protocol and applicable regulatory requirements.

# 20 Trial documentation

# 20.1 Protocol amendments

After the protocol has been approved by the main REC and the MHRA, no changes may be made without the agreement of both the investigator and the sponsor.

The MHRA and main REC do not need to approve any substantial change to the protocol that needs to be implemented urgently to avoid an immediate hazard to trial subjects. The sponsor will ensure that the MHRA and main REC are informed of urgent amendments in accordance with the detailed guidance to EU Directive 2001/20/EC and the standard operating procedures issued by NRES for NHS RECs.

All agreed protocol amendments will be recorded on a written agreement which will be signed and dated by the investigator and sponsor, and attached to the original protocol. The REC and/or MHRA must approve substantial amendments before they are implemented.

The following changes to the trial plan are permitted by this protocol, and will not be considered as amendments.

- (a) Additional visits, for example to monitor blood pressure, will be arranged if there is a potential risk of a drug-drug interaction (see Appendix 1).
- (b) Additional blood or urine samples may be taken for safety tests if required. The total volume of additional blood taken will not exceed 100 mL. Laboratory safety tests will be repeated, if the investigator has any safety concerns.
- (c) Up to 3 additional visits to the clinic will be permitted, in the event of a technical failure and/or it extra safety tests are needed.
- (d) Additional laboratory tests for ECL-cell markers, biomarkers and/or histology will be done on the gastric biopsies, if the results of other tests suggest that additional tests would be worthwhile.
- (e) Stored serum will be used for laboratory tests not yet defined but related to this trial only.
- (f) Visits 3 and 5 may be made up to 2 days before or after the scheduled day. Visits 4, 6 and 7 may be made up to 3 days before or after the scheduled day. Visits 9-12 may be up to 5 days before or after the scheduled day. Patients will be given sufficient YF476 to cover any delays. Therefore, up to 33 days extra YF476 may be taken by each patient, although every effort will be made to arrange patient's visits on the scheduled days.
- (g) It might not be possible to take a video of every gastroscopy. Photographs should suffice.
- (h) If after the first few patients have completed the trial it is clear that increasing the dose at Visit 4 from 50 mg YF476 *once* daily to 75 or 100 mg *once* daily is necessary for a satisfactory response, and that the regimen is well tolerated, subsequent patients may be started on 75 or 100 mg *once* daily at their next visit.
- (i) If after the first few patients a satisfactory response to the 50 mg YF476 dose once daily is seen at Visit 4, the dose may be reduced to 25 mg YF476 once daily, and subsequent patients may be started on this lower dose.

- (j) Follow-up may be extended if:
  - (i) a subject has an unresolved adverse event, which, in the opinion of the investigator, merits further follow-up; or
  - (ii) new information becomes available that supports an extended follow-up period.

The investigator will decide on the nature of the follow-up. For example, subjects may have a telephone follow-up at which they are asked about adverse events, or subjects may be asked to attend extra outpatient visits for additional monitoring of blood levels or effects of IMP, and for extra safety tests. The extra safety tests might include tests that are not described in this protocol. The investigator reserves the right, during or after the study, to do any extra safety tests that are in the best interest of the subjects. Those extra tests may or may not be described in this protocol.

(k) If the patient has not fasted for Visit 1, fasting safety tests of blood and urine may be done at Visit 2.

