#### 2.2 Trial medication

YF476 (50 mg: 2 x 25 mg capsules) by mouth *once* daily for 12 weeks. Taken with breakfast except on clinic visit days when patients will fast overnight and take YF476 after completion of assessments.

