#### 6.2 Screening and treatment periods

	Visit 1: Visit 2:		Treatment period				Visit 7: 12 weeks after
	Screening	Screening 	Visit 3: 3 weeks	Visit 4: 6 weeks	Visit 5: 9 weeks	Visit 6: 12 weeks	stopping YF476
Informed consent	Х						
Medical history	X						
Inform GP	X						
Medical examination	Х			Х		X	
12-lead ECG	Х		Х	Х	Х	X	
Vital signs	Х		Х	Х	X	X	
Safety tests of blood & urine	Х		Х	Х	Х	Х	
Fasting serum gastrin, plasma CgA and serum for storage	Х		Х	Х	X	X	Х
Plasma YF476			$X^7$	X 	X 	X 	
Pregnancy test 	X	X	Х	X	X	X	
H. pylori test 	Х						
Gastroscopy 		X		X 		X 	X 
Collect & check diary card			Х	Х	Х	X	
Collect & check YF476 container for compliance			Х	Х	Х	X	
Issue YF476 capsules		Х	Х	X 	X 		
Issue diary card		Х	Х	X	X		
AE & concomitant medication enquiry			<	<>			

1. Women of child-bearing potential

2. Fasting from food and fluids for at least 6 hours before gastroscopy

3. Patients who meet the entry criteria, start 50 mg YF476 by mouth once daily at home on the day after Visit 2.

4. If gastroscopy at Visit 4 reveals complete regression of carcinoids on visual inspection, stop YF476, omit Visits 5 & 6, and proceed to Visit 7. If gastroscopy at Visit 4 reveals continuing presence of carcinoids on visual inspection, increase dose of YF476 to 75 or 100 mg *once* daily (optional).

5. If gastroscopy at Visit 6 reveals no regression of carcinoids, omit Visit 7.

6. *H. pylori* test will be done according to local SOPs, only if status is unknown.

7. Patients fast overnight before visit and bring their container of YF476 with them. They take YF476 only after collection of blood samples for trough YF476, fasting serum gastrin and CgA levels, and gastroscopy (if applicable). Patients stay 1 h after dosing for collection of blood sample for peak YF476 level

Visit 8 	Visit 9 	Visit 10 	Visit 11 	Visit 12 
Consent to extended dosing.	Safety &	Safety & efficacy	Safety &	Safety & efficacy
Some patients  might have a	efficacy check 	check  & gastroscopy 	efficacy check 	check  & gastroscopy 
new baseline gastroscopy and	after 12 weeks	after 24 weeks of	after 36 weeks	after 52 weeks of

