### 7 Introduction

#### 7.1 Gastrin

Gastrin is a hormone secreted by G cells in the gastric antrum (Dockray *et al* 2001). It has at least two major physiological functions: to stimulate gastric acid secretion and to stimulate growth of the oxyntic mucosa (Håkanson *et al* 1994).

Food stimulates G cells to secrete gastrin into the circulation (Richardson *et al* 1976; DelValle and Yamada 1990). Large increases in blood levels of gastrin occur after food. Circulating gastrin stimulates gastrin receptors (also called CCK-B or CCK-2 receptors) on the enterochromaffin-like (ECL) cells in the gastric fundus, causing those cells to secrete histamine (Konagaya *et al* 2001; Bakke *et al* 2001), which in turn stimulates adjacent gastric oxyntic cells to secrete acid into the lumen of the stomach. Gastric acid secretion is controlled by the action of (H+, K+)–ATPase (the proton pump) in response to stimulation of muscarinic M3 receptors (Aihara *et al* 2003) or histamine H2 receptors (Hersey and Sachs 1995).

Initially, acid secretion is neutralised by the buffering capacity of food. But, as digestion proceeds and the gastric contents are moved into the duodenum, the buffering capacity of the food diminishes and intragastric pH starts to fall. Falling pH stimulates antral D cells to secrete somatostatin (SST), a hormone that switches off gastrin secretion by the G cells (Sanduleanu *et al* 2001).

Acid secretion is also under nervous control, by the vagus. Food causes central stimulation of the vagus, which leads to gastrin release from G cells in the stomach and thereby an increase in acid secretion – the cephalic phase of gastric acid secretion.

[figure not shown]

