# 14 **Procedures and observations**

# 14.1 Visit 1: Screening for eligibility (part 1)

Patients will be asked to fast for 6 hours before this screening visit. The investigator will complete the following evaluation for each subject and enter the data from this visit, and all subsequent visits, on the appropriate page of the CRF:

- informed consent;
- letter to GP;
- medical history (including evidence for diagnosis of CAG, such as pernicious anaemia, achlorhydria, parietal cell antibody, intrinsic factor antibody, endoscopy and biopsy), medical examination, vital signs (heart rate and blood pressure);
- 12-lead ECG;
- *H. pylori* test (if status unknown);
- fasting serum gastrin, plasma CgA and serum for storage;
- laboratory analyses:
  - haematology: Hb, MCV, haematocrit, WBC and differential, and platelets;
  - biochemistry: urea, creatinine, total bilirubin, total protein, albumin, globulin, alkaline phosphatase, AST, ALT, gamma GT, glucose, cholesterol, triglycerides, potassium, sodium;
  - urinalysis: dipstick test: protein, blood, ketones, glucose, leukocyte esterase, specific gravity, nitrites, pH; microscopy if the result of the dipstick test for protein, blood, leukocyte esterase or nitrites is abnormal; urine pregnancy test only in women of child-bearing potential.

The investigator will tell patients to fast before gastroscopy at Visit 2.

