# 14.2 Visit 2: Screening for eligibility (part 2), and start of YF476 treatment

Visit 2 will be within a maximum of 4 weeks after Visit 1. Patients will be asked to fast from food and fluids for 6 hours before this screening visit. The investigator will assess for eligibility all of the patient's results from the first screening visit. Eligible patients will:

- have fasted;
- have a pregnancy test if they are a woman of child bearing potential;
- undergo baseline gastroscopy and gastric biopsies; if the presence of gastric carcinoids is confirmed, the patient will be given the following until the next visit, which will be 3 weeks after Visit 2:

- container of YF476 capsules (25 mg); 2 capsules to be taken with breakfast, starting on the day after gastroscopy; and
- diary card, to record YF476 doses, any adverse events, and any concomitant medication.

It might be possible to combine Visits 1 and 2 for some patients.

The investigator will tell patients to fast before Visit 3, and to bring their container of YF476 capsules with them at the visit.

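### Section 20.1(k) moves only the safety tests to Visit 2 when a patient has not fasted for Visit 1, leaving that patient without a fasted pre-dose gastrin and CgA baseline

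*Protocol*

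**What the plan says.** Section 14.1 lists "fasting serum gastrin, plasma CgA and serum for storage" among the Visit 1 procedures and says: "Patients will be asked to fast for 6 hours before this screening visit". In the Section 6.2 flow chart these samples have their own row, apart from the safety tests. That row is marked at Visit 1 and at Visits 3 to 7, but not at Visit 2. The Visit 2 procedures in Section 14.2 also list no gastrin or CgA sample, although patients fast for that visit: "Patients will be asked to fast from food and fluids for 6 hours before this screening visit".

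Section 20.1 lists changes that are permitted without an amendment. Item (k) reads: "If the patient has not fasted for Visit 1, fasting safety tests of blood and urine may be done at Visit 2".

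On food, Section 7.1 states: "Large increases in blood levels of gastrin occur after food". On analysis, Section 18.1 (Efficacy data) names changes in gastrin and CgA as secondary endpoints and says: "The data during the treatment period will be compared with baseline using ANOVA".

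The length of the fast is stated in more than one way. Section 2.2 says: "Taken with breakfast except on clinic visit days when patients will fast overnight and take YF476 after completion of assessments". Note 7 to the Section 6.2 flow chart, which applies to Visits 3 to 6, says: "Patients fast overnight before visit and bring their container of YF476 with them". Section 13 gives 6 hours without food before every visit, and Section 14.1 gives 6 hours for Visit 1.

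**The concern.** The protocol expects that some patients may not have fasted at Visit 1 and provides a remedy, but the remedy stops at the safety tests. The gastrin value from that visit would be a fed one, set against fasting values at Visits 3 to 6. By the protocol's own account food raises gastrin, so the error has a known direction. YF476 is itself expected to raise gastrin (Section 7.8.5), so an inflated baseline works against the effect being looked for. Treatment starts the day after Visit 2, and after that no fasted pre-treatment value can be obtained. In a trial of at most 10 patients, each lost or distorted baseline counts.

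**Working it through.** **Step 1: is there a fasted replacement anywhere in the protocol?**

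- Item (k) names safety tests of blood and urine only, and makes even those optional.
- Safety tests and gastrin/CgA are separate rows in Section 6.2 and separate bullets in Section 14.1, so the term safety tests does not take in the biomarkers.
- Item 20.1(b) allows additional blood for safety tests. Item 20.1(d) concerns extra tests on biopsies. Neither covers a repeat gastrin or CgA sample.
- The optional new baseline at Visit 8 comes after the first course of treatment, so it is not a pre-treatment value.
- The procedures for Visits 3 to 6 each tell the investigator to check that the patient has fasted. Section 14.1 has no such line for Visit 1.

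So no text gives an unfasted patient a fasted pre-dose gastrin or CgA sample. The exception is a patient whose Visits 1 and 2 are combined (Sections 6.1 and 14.2), because the sample then falls on the fasted gastroscopy day.

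**Step 2: which comparisons use this baseline?**

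| Outcome (Section 18.1) | Baseline taken at | Affected? |
|---|---|---|
| Primary: lesion size or number, or ECL-cell density | Visit 2 gastroscopy and biopsies, fasted | No |
| Histologic grade, biopsy PCR | Visit 2 biopsies, fasted | No |
| Serum gastrin (secondary) | Visit 1 | Yes, in unfasted patients; direction known |
| Plasma CgA (secondary) | Visit 1 | Sample not fasted as specified; no food effect documented |

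**Step 3: how large could the gastrin error be?**

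The protocol gives no figure to reproduce and no fed-to-fasting ratio. What follows is illustrative. Let r be the fed value divided by the fasting value (assumed 1.5 to 3), and k the number of affected patients out of n = 10 (the maximum in Section 18.2; k is assumed).

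For one affected patient, the ratio to baseline is divided by r, an error of 1/r - 1:

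- r = 1.5: 1/1.5 - 1 = -33%
- r = 3: 1/3 - 1 = -67%

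For the group, the geometric-mean baseline is inflated by r^(k/10), so the ratio to baseline shifts by r^(-k/10) - 1:

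| r | k = 1 | k = 3 |
|---|---|---|
| 1.5 | -4.0% | -11.5% |
| 2 | -6.7% | -18.8% |
| 3 | -10.4% | -28.1% |

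With an assumed true rise of 50% and r = 2, the apparent rise is 1.5/2^(0.1) - 1 = +40.0% for k = 1 and 1.5/2^(0.3) - 1 = +21.8% for k = 3. With k = 0 the error is zero.

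**Step 4: blood volume of a repeat sample (Section 14.14).** Gastrin and stored serum 2 × 2.5 mL, plus CgA 4 mL, gives 9 mL.

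**The case against.** The strongest reply is that the protocol never authorises a fed gastrin baseline. Sections 6.2 and 14.1 specify a fasting sample, Section 13 requires a fast before each visit, and item (k) is merely silent on gastrin. That is fair, and it limits the point: the defect is a missing replacement sample, not permission to use a fed one. It does not remove the defect, because item (k) exists precisely for the case in which the fasting instruction was not followed.

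A second reply is that a value known to be unfasted can be set to missing or left out of a sensitivity analysis, and that a model with visit fixed and subject random can tolerate a missing visit. This also stands, so it would be wrong to say that no analysis can deal with the problem. But it needs fasting status to have been recorded, and it gives up that patient's change from baseline.

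Third, the size rests on assumption. Section 7.1 describes normal physiology, whereas these patients have achlorhydria and sustained hypergastrinaemia (Section 7.4.1), and the protocol gives no fed-to-fasting ratio for them. This stands as well.

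A reader might go further in three ways that the protocol does not support:

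- That every comparison with baseline is biased. It is not: the endoscopic, histological and biopsy-PCR baselines come from Visit 2.
- That a fed sample biases CgA. The protocol documents no food effect on CgA, so neither direction nor size can be claimed.
- That a 6-hour fast at baseline against an overnight fast on treatment biases the results for all patients. Section 13 sets the same 6-hour minimum for every visit, and nothing in the protocol shows that gastrin or CgA differs between the two. This is an inconsistency in wording.

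**Conclusion.** The point holds as a gap in item 20.1(k). A patient who has not fasted for Visit 1, and whose Visits 1 and 2 are not combined, has no fasted pre-dose gastrin or CgA value, and none can be obtained after dosing begins. The consequence is confined to two secondary biomarker comparisons, and to such patients, in an exploratory pilot. Section 18.1 itself drops the ANOVA if data are insufficient.

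For gastrin the direction follows from the protocol: a fed baseline is too high, which understates the expected rise or shows a false fall. It would not manufacture a rise. The size is not known. Under the assumed ratio of 1.5 to 3, one affected patient in 10 shifts the geometric-mean ratio by -4% to -10%; if all patients fast, the shift is zero. The change is worth making because it is cheap and the baseline is otherwise unrecoverable.

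**What to change.** Extend item 20.1(k): if the patient did not fast for Visit 1, fasting gastrin, CgA and stored-serum samples are also taken at Visit 2, before the first dose, and the fasted values are the baseline. Mirror this in the Section 6.2 flow chart and in Section 14.2, and record fasting status at Visit 1 so that the patients concerned can be identified.

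The cost is about 9 mL more blood for those patients, at a visit for which they already fast and at which item (k) already allows a blood sample. State this volume explicitly, because the overage in Section 14.15 and the allowance in item 20.1(b) are worded for safety tests only.

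Separately, reconcile the fasting length for gastrin and CgA samples across Sections 2.2 and 6.2 note 7 (overnight) and Sections 13 and 14.1 (6 hours), so that one length applies to all of them. This is a change of wording only.
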